7 RANDOMISATION AND BLINDING

A random allocation sequence will be computer-generated (Intercooled Stata 9.2) and concealed from all investigators throughout the study. The random assignment to intervention group will be provided by the MSHR statistician. Block randomisation will be used to maintain similar numbers of participants in the intervention and control groups and to minimise the potential influence of time of enrolment. Allocation will be stratified by place of TB diagnosis (hospital or clinic) and ethnicity (Papuan/non-Papuan), the latter because of the different Vitamin D status of these two groups (as per preliminary data). Allocation concealment will conform to the revised CONSORT guidelines which take account of the logistically challenging environment at the study site (82). We have successfully used this method in over 1,200 malaria patients (three RCTs) in Timika (1, 2, 4). The random allocation will be in sealed, opaque envelopes in two boxes (Papuan and non-Papuan) in each study location. Prior to opening the envelope, the investigator will complete the randomisation form to check if the patient is eligible for enrolment, obtain informed consent and complete the enrolment questionnaire.

Placebo will be compounded to be indistinguishable by appearance, smell and taste from the matching active medication. All study personnel and participants will be blinded to treatment assignment for the duration of the study. Only the study statistician and the Data Safety Monitoring Committee will see any unblinded data and these individuals will not have contact with study participants. The randomisation code will be kept at MSHR by an independent person unrelated to the study. The randomisation sequence will not be broken until primary outcomes have been measured and agreed by the study investigators.

8 ETHICAL CONSIDERATIONS

8.1 Randomised controlled trial design

The perceived withholding of a potentially beneficial medication to half the enrolled study participants may arise as an ethical consideration. To alleviate these concerns, we will explain in advance very clearly to staff, community leaders and patients: (a) the necessity for the blinded, randomised, placebo-controlled approach, and (b) the fact that there is as yet no evidence of benefit of L-arginine and/or vitamin D supplementation in TB, and hence those receiving placebo will not necessarily be disadvantaged. The verbal and written information provided by local research assistants and interpreters will explain the fact that half the patients enrolled will not get the active study drug. Patients will be reminded that they can withdraw from the study at any time without compromising their care or relationship with clinic staff. We have successfully employed blinded RCT design in the local population in large malaria trials to date, with patients willing to participate in such a study design.

All patients, including those who decline to participate in the study, will continue to receive all aspects of standard TB care. They may in fact experience improved care due to greater attention being given to

the importance of TB medication adherence, quality control aspects of the study which will spill over into general practice, and the presence of extra staff (i.e. research assistants and study investigators) being able to provide operational and medical assistance at the clinic.

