TB, caused by *Mycobacterium tuberculosis* (MTB) is a disease of major public health significance to Indonesia. Our goal is to achieve better treatment outcomes in pulmonary tuberculosis (PTB) through simple and cost-effective interventions. Improvement in TB treatment resulting from successful adjuvant therapy has the potential to decrease duration of infectivity, disability, and duration of antimicrobial treatment. Each would have major clinical and public health benefits. Two major pathways by which human macrophages kill MTB are the arginine-nitric oxide (NO) and Vitamin D pathways. Both NO and activated vitamin D are potent mycobactericidal agents *in vitro*. We therefore propose a clinical RCT to investigate the *in vivo* potency of L-arginine and vitamin D, the substrates for these two major candidate human mycobactericidal pathways, in clearing mycobacteria from sputum and improving clinical outcomes.

A summary of the proposed studies is shown in diagrammatic form in Figure 1. The main study is a randomised controlled trial: 'Arginine or Vitamin D Adjuvant Therapy in Pulmonary Tuberculosis' - the ADAPT Study. In this study we will enrol 444 consecutive newly diagnosed sputum smear positive pulmonary TB patients from two sites in Timika, Papua Province, Indonesia. Patients will be commenced on standard TB treatment and in addition, those who agree will be randomised into four groups (arginine/placebo, vitamin D/placebo, arginine/vitamin D or placebo) and followed for six months. A series of clinical, haematological, microbiological and pulmonary function measurements will be made to assess treatment outcome. The primary outcome measures of sputum culture at 1 month and pulmonary function 2 months after commencing treatment. Related studies include:

- **1.** Economic analysis;
- **2.** Survey of extrapulmonary TB;
- **3.** Evaluation of the burden of TB-HIV co-infection;
- 4. Evaluation of a rapid diagnostic TB antigen test, and
- **5.** Evaluation of healthy non-TB infected control subjects in order to gain normal reference range values for the RCT outcome measures.

The proposed research program will include significant capacity building opportunities, including 2 PhDs, 1 Masters and a range of professional training opportunities in Indonesia and Australia.

[figure not shown]

Figure 1: Diagrammatic Representation of Proposed Tuberculosis Research Programme in Timika

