3.3.3 Study Medications

3.3.3.1 Medication administration

At enrolment, patients will be randomly assigned to one of three groups:

- 1) Group 1: supplementary **L-arginine** 6g daily for eight weeks plus **placebo vitamin D**₃ once every four weeks for two doses (0 and 4 weeks);
- Group 2: supplementary L-arginine 6g daily for eight weeks plus vitamin D₃ (cholecalciferol) 50 000 IU (1250mcg) once every four weeks for two doses (0 and 4 weeks);
- Group 3: placebo L-arginine daily for eight weeks plus vitamin D₃ (cholecalciferol) 50 000 IU (1250mcg) once every four weeks for two doses (0 and 4 weeks);
- Group 4: placebo L-arginine daily for eight weeks plus placebo vitamin D₃ every four weeks for two doses (0 and 4 weeks);

Study drugs will be administered separately from the pre-packaged TB medications, provided in standard Indonesian NTP 'Combipacks' (fixed dose combination therapy for TB).

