5 STATISTICAL ANALYSES

5.1 Sample size

Sample size has been calculated using the graphical method for 2x2 factorial designs informed by the Fleiss equation, described by Byth and Gebski (71). Making a conservative assumption of sub-additive interaction between the 2 interventions (interaction coefficient of 0.5), then at a level of significance of 5%, a sample size of 444 (111 participants in each arm) will provide 82% power to demonstrate that each treatment results in a 20% reduction in the proportion culture positive at one month (from 60% to 40%), assuming loss to follow up of 10%. As there have been no trials of co-administration of vitamin D and L-arginine, the characteristics of potential immunological interactions can be extrapolated only from in vitro macrophage studies, in which findings conflict: vitamin D was found to inhibit iNOS expression in one study(44); yet upregulate NOS2A in another (68); the latter study also found the suppressive effect of vitamin D on MTB replication to be partially impaired if NO formation was inhibited. Including a sub-additive interaction term in the sample size calculation provides a margin a caution; if there is minimal or no interaction between the two interventions, our power will be greater. A factorial design rather than a three-arm study allows us to investigate whether if is safe and effective to co-administer the two interventions. Acknowledging the possibility of statistical interaction between the terms, we have an *a priori* plan to analyse primary and secondary outcomes according to subgroups receiving single interventions as well as according to the overall factorial model (71).

Mean time to culture negativity in mostly drug sensitive TB is 32 days (New York) (72) -57 days (Turkey) (73). Based on bacillary burden and extent of cavitatory disease, we estimate a minimum of 60% of Timika patients will be culture positive at 1 month. Our power will be increased if this proportion is higher. This sample size will also be powered to detect a 9% absolute difference in the mean improvement in percent predicted FEV1, a component of the composite endpoint, at 6 months. Mean baseline percent predicted FEV1 in Timika is 63.6% predicted (SD 22) rising to 77.9% predicted (SD 23) at 6 months. Each month, at least 25 eligible smear positive pulmonary TB patients are diagnosed and treated at the Timika study site. If 90% agree to be enrolled, recruitment will take <2yrs to complete.

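### Section 8.1 describes half the patients as not getting the active study drug, but in this four-arm design that holds only for each drug separately; one in four gets no active drug

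*Protocol*

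**What the plan says.** Section 8.1 deals with the ethics of a placebo-controlled design. It opens with the concern it means to answer: "The perceived withholding of a potentially beneficial medication to half the enrolled study participants" may be raised as an ethical issue. It then commits the local research assistants and interpreters to specific content. The verbal and written information "will explain the fact that half the patients enrolled will not get the active study drug".

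The design is described elsewhere. The Executive Summary says that consenting patients will be "randomised into four groups (arginine/placebo, vitamin D/placebo, arginine/vitamin D or placebo"). Section 3.3.3.1 defines the groups by dose. Its lead-in reads "At enrolment, patients will be randomly assigned to one of three groups", but four numbered groups follow:

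- Group 1: active L-arginine with placebo vitamin D ("6g daily for eight weeks plus placebo vitamin D")
- Group 2: both active drugs ("Group 2: supplementary L-arginine 6g daily for eight weeks plus vitamin D")
- Group 3: placebo L-arginine with active vitamin D
- Group 4: placebo for both

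Section 5.1 gives the allocation: "a sample size of 444 (111 participants in each arm"). Section 3.3.3.4, on stopping study medication, refers to two study drugs. Section 1.1.8 records that the design was changed from three arms to a four-arm factorial.

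**The concern.** The sentence in section 8.1 reads like a description of a one-drug trial with equal active and placebo arms. This trial has two drugs and four arms. A participant told that half will not get the active study drug would naturally take this to mean an even chance of receiving nothing but placebo. Under the stated design that chance is one in four.

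What is at stake is the accuracy of what participants are told before consenting. Section 8.1 presents the statement as a fact to be conveyed, so staff who follow the protocol as written would pass on a wrong allocation figure. The figure also gives no hint that one arm receives both drugs. That arm deserves a clear description, because section 5.1 says "there have been no trials of co-administration of vitamin D and L-arginine" and gives the safety of giving the two together as one reason for the factorial design.

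**Working it through.** This is a count over the planned arms; no sample-size formula is involved.

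**Inputs**

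| Arm (section 3.3.3.1) | L-arginine | Vitamin D | Planned n (section 5.1) |
|---|---|---|---|
| Group 1 | active | placebo | 111 |
| Group 2 | active | active | 111 |
| Group 3 | placebo | active | 111 |
| Group 4 | placebo | placebo | 111 |

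Total: 4 × 111 = 444, which matches section 5.1.

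**Trying to reproduce the stated half**

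- No active drug at all: Group 4 only, 111/444 = 25%. This does not give half.
- At least one placebo: Groups 1, 3 and 4, 333/444 = 75%. This does not give half.
- Not given L-arginine: Groups 3 and 4, 222/444 = 50%. This gives half.
- Not given vitamin D: Groups 1 and 4, 222/444 = 50%. This gives half.

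Half is therefore the margin for one named drug at a time. It is not the share who go without active treatment.

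**The full split**

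- Neither drug: 111/444 = 25%
- Exactly one drug: 222/444 = 50% (L-arginine only 25%, vitamin D only 25%)
- Both drugs: 111/444 = 25%
- At least one drug: 333/444 = 75%
- Each drug separately: 222/444 = 50% receive it

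Read as the share with no active drug, the stated figure is twice the designed one (50% against 25%). It also puts the share on some active drug at 50%, where the design gives 75%.

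**The case against.** The best defence is that half is right for each drug. The opening sentence of section 8.1 speaks of withholding a medication, with the indefinite article, and that is true of L-arginine and of vitamin D in turn. On this view one sentence merely omits the word each. This stands for the opening sentence, which needs only light rewording. It does not rescue the sentence on what participants will be told. That sentence refers to one active study drug, names neither, and does not say that the figure applies to each, in a protocol that elsewhere counts two study drugs.

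Some stronger readings are tempting, but the documents do not support them.

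- *That exposure to each drug's own risks is understated.* It is not. The gastrointestinal effects of L-arginine can arise in Groups 1 and 2, and vitamin D hypercalcaemia in Groups 2 and 3. Each pair is 222/444 = 50%, so half is the right chance for each of these risks. Only the chance of receiving at least one drug, or both, is not conveyed.
- *That participants are not told about the combination arm.* This cannot be asserted. The information and consent sheets (Appendices 3 and 4) are not in the copy reviewed. Section 8.1 gives one item of the information, not all of it, and section 3.3.1 promises a detailed explanation of what the study involves. The sheets may well describe all four groups.
- *That half and the count of three groups are leftovers of the same superseded design.* Section 1.1.8 makes this plausible for the count of three. For half there is no such evidence: with equal allocation, which is an assumption because the old ratio is not given, a three-arm design would have had one third on placebo only. The documents do not say where half came from.

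It is also fair to say that the count of three in section 3.3.3.1 is unlikely to mislead anyone, since four groups are listed directly below it.

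**Conclusion.** The point holds, in a limited form. The sentence in section 8.1 is wrong as written: it is true only of each drug separately, and the share with no active drug is 25%, not 50%. At least one active drug goes to 75%, and both drugs to 25%. These figures rest on the four equal planned arms in section 5.1; actual numbers after blocked, stratified randomisation may differ slightly, which does not change the conclusion.

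The defect lies in what the protocol commits staff to tell participants. Whether it reaches them depends on the information sheets, which could not be checked. Allocation, sample size, power and analysis are unaffected. The count of three groups in section 3.3.3.1 is a separate clerical slip. The correction should be made because the statement concerns consent and is cheap to put right.

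**What to change.** 1. In section 8.1, replace the sentence on what the information will explain with the four-way split. For example: *one in four patients will receive L-arginine only, one in four vitamin D only, one in four both, and one in four neither; so half will receive each drug, and three in four will receive at least one.*
2. Reword the opening sentence of section 8.1 to match, or make it say that each medication is withheld from half the participants.
3. Check the participant information sheets, in both languages, against the corrected text and amend them only if they differ.
4. In section 3.3.3.1, change the count of groups in the lead-in from three to four.

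The cost is a few words in two sections, a check of the sheets, and notification of the ethics committees. No dose, procedure, sample size or analysis changes.

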8.2 Potential for harm arising from study medications

Although anticipated to be unlikely, potential medication side effects will be monitored as detailed in 6.1, 6.2 and Appendices 5 and 6.

8.3 Disincentive due to requirements of study participants

Impacts on participants include the extra medications (active study drug or placebo) and the extra investigations required. The baseline evaluations (standard TB clinic questionnaire, collection of sputum sample, provision of information for informed consent, anthropometric measures, chest radiograph, 6 minute walk, eNO, lung function, modified St George Respiratory Questionnaire) are estimated to take approximately 1 hour per patient. Further appointments of similar duration will be required at 4, 8 and 24 weeks when some of these measures are repeated, but all other follow up visits will be much shorter. It is already routine according to NTP protocols for TB patients undergoing treatment to have a baseline questionnaire, clinical assessment, 3 sputum specimens and chest x ray, then monthly weight, repeat chest x ray and sputum collections at 2 and 6 months, and regular recording of symptoms, adherence and side-effects. The additional time required at the clinic could potentially serve as a disincentive for patients to attend for TB treatment. These extra requirements will be explained at the time of enrolment. In addition, we will be careful to question patients about whether this is the case, offer flexibility regarding time and day of the week on which they can attend, ensure efficiency in carrying out the investigations, and ensure that those who skip some measures, or withdraw altogether, continue to receive their TB therapy.

8.4 Potential for harm arising from baseline and follow up measurements

Measurements will be performed in the purpose-built open-air clinic annex. The filters used with both the spirometry and eNO will prevent transmission of TB. Standard occupational health and safety standards for staff will be upheld, including safe practices in biohazard disposal.

8.5 Feasibility of continuation after study completion

Vitamin D and L-arginine are relatively cheap and readily available and therefore, if shown to be beneficial, would be able to be utilised as adjuvant treatments after completion of the trial at the study site, more widely in Indonesia and potentially in similar settings in other countries.

8.6 Confidentiality and Data storage

All data collected from individuals will be stored confidentially on password-protected computers accessible only to the named investigators, data entry clerks and named research students. Paper records will be stored in locked filing cabinets at the NIHRD-MSHR research building in Timika. We appreciate the risk of loss of data due to computer failure or power blackout and as per our current studies, data will be backed up at least weekly, sent to and stored at the collaborating institutions.

9 QUALITY CONTROL AND QUALITY ASSURANCE

The NIHRD and Menzies School of Health Research will have co-ownership of the data, consistent with the Memorandum of Understanding and with previous practice of other collaborative studies between our two institutions. The research team will be working on the basis of this protocol and the NTP manual. The team from NIHRD and MSHR/ANU will evaluate and assess the work to ensure a high standard procedure applies to this study and ensure the collection of high quality data.

9.1 Eligibility criteria

[name] will perform weekly checks on all enrolment forms to ensure that the correct diagnostic criteria have been applied and that only patients eligible for inclusion have been included. These will be cross-checked by [name] (NHIRD).

9.2 Informed consent process, including refusal rate and withdrawal rate

The local investigators [name] and [name] will perform weekly checks on all consent forms to ensure that the correct procedures have been followed and that informed consent has been obtained in the manner set out in this protocol.

9.3 Randomisation process

Local investigators will perform weekly checks to ensure that patients have been randomised in the correct manner set out in this protocol. The principal investigators will carry out spot checks on eligibility and the informed consent and randomisation processes during regular visits to Timika.

9.4 Accuracy of data collection and data entry

All data will be double entered and discrepant data will be checked with primary sources. [name] and [name] will carry out spot checks of data collection forms and check the accuracy of information directly from the patient.

9.5 Adverse events related to the study or to TB treatment

Research team members at the TB clinic and at RSMM will report all potential adverse events to the treating doctor and the local investigators ([name] and [name]) immediately. Presumed TB medication side effects will be reported to the treating physician as soon as possible, the strategy outlined in Appendix 5 should be followed, and if necessary, an Adverse Drug Reaction form completed by the treating doctor (Appendix 6). These will be reviewed by [name] and [name]. Any serious adverse effects will be reported immediately to the principal investigators and the chair of the Data and Safety Monitoring Committee.

9.6 Data and Safety Monitoring Committee

A Data and Safety Monitoring Committee has Indonesian and Australian membership consisting of experienced researchers and health practitioners independent of the research team (NIHRD nominee,

[name], Specialist Physician and Endocrinologist, MSHR, [name], Statistician, ANU and [name], Clinical Director, RSMM Hospital, Timika). They will review the progress of the study and give advice to the research team on two occasions during the study. They will have the power to immediately discontinue the study if severe adverse events attributable to the study medications occur.

10 DATA HANDLING AND RECORD KEEPING

Data will be held in Timika for the duration of the trial, paper in a locked filing cabinet and electronic data in a password-protected regularly backed-up file. Back-up copies of data will be regularly sent as required by the relevant ethical committees and for safe-keeping in electronic format to investigators directly involved in this research at NIHRD (Jakarta), MSHR (Darwin) and ANU (Canberra).

The field data collected will be held by the principal investigators for 10 years after publication, in accordance with international best practice requirements and then destroyed.

11 FINANCING

Financing has been secured (subject to ethical approval) from the following sources indicated in Table 4. Funding bodies have indicated that funds need to be spent by the dates indicated. In particular, major in-kind contributions have been committed by the out-going MALKON director, with the expectation of use of funds commencing prior to his departure in June 2008. Pending applications are listed, and further funding applications will be made as appropriate during subsequent years of the TB project.

Equipment	Cost \$ AUD
e.g. Niox Mino® Unit, Sensorpack and NO cylinder; lung	15 600
function testing accessories.	
Study medications	
Active and placebo L-arginine and vitamin D	11 392
On-site Specimen Collection And Processing (Timika)	
Blood, sputum	13 052
Off-site Specimen Collection And Processing (Australia))
e.g. PBMC, 1,25(OH)2D3, PTH, amino acids, sputum	Costs partly absorbed by NHMRC program
	grant
Travel and local study site wages	From 2008 ARC submission
Study Participant Incentives (travel costs, snack)	\$120 000

Table 3: Funding Requirements

Table 4: Funding Sources

Funding Source	Purpose	Time frame for use	Value \$ AUD
